## 2.) PHASE 2: INTERVENTION TRIAL

*Aim 2: Determine the impact of tailored messaging via personal health record on adherence to anti-thrombotic therapy and health outcomes in people living with AF.*

*Aim 3: Determine the feasibility of measuring medication adherence with queries to electronic prescribing software and use of ‘smart’ pill bottles.*

During the last 12 months of our study, we will conduct a 6-month trial of the intervention designed and built in Phase 1 of the study to examine the impact on patient engagement and medication adherence. Patients who meet inclusion criteria and agree to participate will be randomly assigned to one of two groups – Experimental or Control. The research team will alternate random assignment to experimental or control group in order to achieve equal numbers of patients receiving VKA and NOAC medication across both groups. Please see Figure 2 below, outlining the study group assignment process.

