## RESEARCH DESIGN AND METHODS

There will be two phases in this study. In the first phase, we will use a patient-centered approach to design and build a PHR based educational intervention based on patient preferences for content, timing and delivery mechanism. In the second phase, we will test the intervention in a six-month randomized controlled trial.

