**Figure 2: Tech Trial Study Group Assignment Process**

### ***i. Patient Selection***

- a) Study Population: The study population is comprised of all adult, ambulatory PPG-Cardiology patients with non-valvular atrial fibrillation who are taking an oral anti-coagulant medication
  
- a. Sample Size: Approximately 160 patients (80 Control/80 Experimental Groups; randomized/un-blinded)

\*Based on prior data, the within-group standard deviation of the medication possession ratio (MPR) is estimated to be 10%. MPR is considered a continuous variable and sample size calculations are based on comparing the difference in two mean MPR values. With a final sample size of 64 subjects per group completing the study, the study will have 80% power to detect a 5% difference in MPR between groups, assuming two-sided tests each conducted at a 5% significance level. To account for a 20% dropout rate, 80 subjects will be enrolled per group.

b) Inclusion/Exclusion Criteria:

Inclusion Criteria

1. Diagnosis of Atrial Fibrillation (Paroxysmal, Persistent, Permanent)
2. Receiving Oral Anticoagulation (VKA or NOAC) for non-valvular AF
3. Physically and Mentally capable of providing Informed Consent
4. Age 18 years or older
5. Access to Computer and Internet
6. Ability to read and understand English
7. Current Patient of PPG-Cardiology
8. Willing to have a MyChart account

Exclusion Criteria

1. Absence of History of Atrial Fibrillation (AF)
2. Does not meet Inclusion Criteria
3. Anticoagulation with VKA or NOAC for reasons other than non-valvular AF
4. Prescribed the anticoagulation medication Dabigatran, as this specific NOAC cannot be transferred from its original pill bottle to the study smart pill bottle
5. Unable to physically or cognitively carry out the tasks necessary for utilizing a PHR such as; blindness, loss of function of arms, cognitive impairments (per chart review) that would interfere in learning a new task
6. Designated as part of a vulnerable subject population that the investigator or designee identifies to have compromised autonomy related to potential study participation
7. Currently participating in another Parkview study that involves PHR use
8. Not willing to have a MyChart account

9. Previously participated in the study focus groups
10. Previously participated in the study design sessions

c) Enrollment:

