A list of adult patients who meet inclusion criteria will be provided by the Anticoagulation Therapy Unit (ATU) Clinic and Parkview Physicians Group-Cardiology. An additional list of adult patients who meet inclusion criteria will be obtained from patient records at Parkview Physicians Group-Cardiology using Epic reporting tools. Research staff will also recruit participants during education sessions held by the Parkview Heart Institute, which have been funded by Boston Scientific. The research staff will be introduced by the Parkview Heart Institute coordinator, but will not present at any time during the education session. Attendees of the education sessions will be given an information folder already provided by the Parkview Heart Institute. The research team has permission to include a flyer (see attached flyer), that can be included in the folder, which provides a short summary about the study. The research team will also distribute recruitment flyers to individuals who may be interested in participating in the study that are in attendance at the education session. Those attendees who express an interest in participating will have their contact information recorded by the research team or will contact the Informatics Research Nurse coordinator as listed on the flyer. As with all possible participants, research staff will review patient charts to identify if they meet inclusion criteria, or if factors in the exclusion criteria are identified. This study will not affect patient standard of care. Before contacting patients, the study nurse coordinator will contact Parkview Physicians Group-Cardiology physicians to inform them of the study and receive permission to recruit their patients for the study. Eligible patients will be contacted by research staff during scheduled ambulatory care visits or contacted by telephone. Eligible patients may also be notified of the study through MyChart, email, or letter and directed to contact research staff by phone if interested in participating. Patients may decide to proceed with the informed consent process at the time of the office visit or schedule another appointment for the study. If the communication is by telephone, appointments will be made at a time convenient for the patient to undergo the informed consent process and patients will be mailed a copy of the informed consent to review prior to their scheduled appointment. Patients will undergo the informed consent process during their appointment and those who meet

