Alcohol Use	Y/N	EHR	Risk for Bleeding: HAS-BLED		√	
Arterial embolus	Y/N	EHR	Health outcome	6 mo. – Baseline		Baseline – 6 mo.

Hemorrhage	Y/N	EHR	Health outcome	6 mo. – Baseline		Baseline – 6 mo.
Hospitalizations	Y/N	EHR	Health outcome	6 mo. – Baseline		Baseline – 6 mo.
Stroke	Y/N	EHR	Health outcome	6 mo. – Baseline		Baseline – 6 mo.
Death	Y/N	EHR	Health outcome	n/a		Baseline – 6 mo.
Calls to Anticoagulation Treatment Unit (ATU)	Numeric	ATU	Burden/ Patient Engagement	6 mo. – Baseline		Baseline – 6 mo.
Prescription Refill Frequency	Numeric	EHR	Assess medication adherence	6 mo. – Baseline		Baseline – 6 mo.
Smart Pill Bottle Use	Numeric	Report	Daily report of pill bottle opening, date/time stamped		√	√
MAS	Numeric	Survey	Assess medication adherence		√	√
PAM	Numeric	Survey	Assess patient engagement		√	√
SUS	Numeric	Survey	Computer use self-efficacy		√	√
AF Knowledge Scale	Numeric	Survey	Assesses knowledge of AF disease		√	√
New Vital Sign	Numeric	Survey	Assesses health literacy		√	√
ACE	Numeric	Survey	Assess patient engagement		√	√
TUPI	Numeric	Survey	Assess patient personality			√
PHR Login Frequency	Numeric	EHR	Assess engagement	6 mo. – Baseline		Baseline – 6 mo.
PHR webpage and video view frequency	Numeric	EHR	Assess engagement			Baseline – 6 mo.
PHR messages/phone calls to study staff	Numeric/Qualitative	EHR	Burden/ Patient Engagement			Baseline – 6 mo.
Appointments scheduled	Numeric	EHR	Assess engagement			Baseline – 6 mo.

\*See Appendix for scoring of HAS-BLED risk for bleeding and CHA2DS2\_VASc risk of stroke

d) Qualitative Data Collection and Analysis:

We will conduct semi-structured interviews at the conclusion of the 6-month study period with all participants in both the control and experimental groups. This data will act to fill the gaps that remain in survey data, as it allows for a deeper examination of particular issues with people living with AF. Participants will be asked questions in order to flesh out more detail around the usage patterns of the tested technologies, patient engagement, technology acceptance and experience with patient-provider communication.

All interviews will be audio recorded, with participant permission and researchers will take field notes. Investigators will review the transcribed digital recordings and field notes and perform thematic analysis to develop

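### Phase 2 assignment is described as both random and alternating; taken literally, alternation lets staff in an un-blinded trial foresee the next arm

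*Protocol*

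**What the plan says.** Three places in the protocol describe assignment as random:

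- Research Design and Methods, on Phase 2: "we will test the intervention in a six-month randomized controlled trial".
- Phase 2: Intervention Trial, opening paragraph: those who qualify and "agree to participate will be randomly assigned to one of two groups".
- Phase 2, Patient Selection, sample size: "Approximately 160 patients (80 Control/80 Experimental Groups; randomized/un-blinded".

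The sentence that follows the second of these gives a mechanism: "The research team will alternate random assignment to experimental or control group in order to achieve equal numbers of patients", the patients in question being VKA and NOAC users, balanced across both groups. It then points to a diagram: "Please see Figure 2 below, outlining the study group assignment process".

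On who recruits, the Enrollment part of Phase 2 Patient Selection says "research staff will review patient charts to identify if they meet inclusion criteria", and "Eligible patients will be contacted by research staff during scheduled ambulatory care visits or contacted by telephone". Consent may take place at the office visit or at a later appointment.

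**The concern.** Under alternation the next assignment is fixed by the last one. Under random assignment it is not. A single procedure cannot be both, and site staff could carry out the sentence in either way.

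If staff alternate, three features of the protocol make this matter. The research team makes the assignment. The trial is un-blinded, so past assignments can be seen. Research staff also screen charts, contact patients and arrange consent. Some eligibility decisions need judgement: exclusion 5 rests on a chart-review view of cognitive impairment, and exclusion 6 on what the investigator or a designee identifies. Staff who can foresee the arm could influence, even without intent, who is approached and when. Assigning only after the patient agrees does not prevent this, because the arm is already known. Alternating separately within VKA and NOAC does not hide it either, because drug class is in the chart before consent.

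What is at stake is the between-group comparison of adherence under Aim 2.

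**Working it through.** **1. The protocol's own figure.** Inputs from Phase 2, Patient Selection: SD of MPR 10, difference 5, two-sided 5%, 64 completers per group, 20% dropout. The two-sample t-test needs 63.8 per group, so 64; power at 64 is 0.801. Enrolment is 64 / (1 − 0.20) = 80 per group. The stated sample size reproduces, and this concern does not touch it.

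**2. How predictable the next arm is, over 160 patients.** The guesser knows all earlier assignments and, for random lists, picks the arm that is behind.

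- Alternation, one list: only the first assignment is unknown, so (159 + 0.5) / 160 = 99.7%.
- Alternation within VKA and within NOAC: (158 + 2 × 0.5) / 160 = 99.4%.
- Random lists, by simulation (block sizes are assumed): fixed blocks of 4, about 71%; mixed blocks of 4, 6 and 8, about 68%; simple randomisation, 50%.

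**3. What a selection shift would do to the type I error.** The protocol gives no shift, so 1, 2 and 3 MPR points are assumed, with no true effect. The standard error is 10 × √(2/64) = 1.768. Rejection is taken from the noncentral t with 126 degrees of freedom and noncentrality shift / 1.768.

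| Assumed shift | Noncentrality | Two-sided rejection |
|---|---|---|
| 1 | 0.57 | 0.087 |
| 2 | 1.13 | 0.202 |
| 3 | 1.70 | 0.391 |

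**4. How much baseline adjustment recovers.** Table 3 collects "Prescription Refill Frequency" and PHR logins for the six months before the trial, and MAS, PAM and ACE at baseline. Assume that selection acts on a trait that drives the baseline measure and follow-up MPR equally, and that the two correlate at *r*. Covariate adjustment then leaves a bias of shift × (1 − r), with residual SD 10 × √(1 − r²) and 125 degrees of freedom.

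| Shift | r | Bias left | Residual SD | Rejection |
|---|---|---|---|---|
| 1 | 0.5 | 0.5 | 8.66 | 0.062 |
| 2 | 0.5 | 1.0 | 8.66 | 0.099 |
| 3 | 0.5 | 1.5 | 8.66 | 0.163 |
| 2 | 0.3 | 1.4 | 9.54 | 0.131 |
| 2 | 0.7 | 0.6 | 7.14 | 0.076 |

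A 6,000-run simulation of the adjusted analysis at r = 0.5 gave 0.059, 0.095 and 0.153, close to the formula. Adjustment helps but does not restore 5%, and it does nothing for traits that the baseline measures miss.

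**The case against.** The strongest reply is that one loosely chosen verb is being made to carry too much. What is alternated is, literally, random assignment. The aim is balance by drug class, which a single A-B-A-B sequence would not secure, and three other statements say random. The sentence may be a clumsy description of stratified or blocked randomisation, and Figure 2 may show exactly that. This stands as a limit: the text does not prove that alternation was intended. It does not exclude it either, because alternation within each drug class would also deliver the balance.

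A second point is timing. The 99% applies at the moment of assignment, whereas many patients are contacted earlier by phone, message or letter. Table 1 gives the trial about 12 months. With 6 months of follow-up, that leaves roughly 6 months to enrol 160, or about 6 a week. If λ other patients of the same drug class enrol between contact and consent, and this number is Poisson (an assumption), predictability at contact is (1 + e^(−2λ)) / 2: 68% at λ = 0.5, 57% at λ = 1 and 50% at λ = 3. This narrows the exposure. It does not remove it, because same-day office consent, the consent visit itself and the scheduling of appointments remain open to influence.

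Third, no passage says that the individuals who recruit see the assignment log, and nothing links a guess rate to a shift of a given size. Both are fair. The error rates above show sensitivity only; they do not estimate this trial's risk.

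**Conclusion.** The concern holds. The protocol states two incompatible assignment procedures, and the one it spells out would, if followed literally, make about 99% of assignments foreseeable at the point of assignment to anyone who knows the earlier ones. That opens the Aim 2 comparison to selection bias; it does not show that bias occurred. With assumed shifts of 1 to 3 MPR points, the 5% error becomes about 9% to 39% unadjusted and about 6% to 16% after adjustment at an assumed correlation of 0.5.

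The conclusion rests on a literal reading of *alternate*, on recruiting staff knowing past assignments (inferred from the un-blinded design and the shared team), and on Figure 2 not saying otherwise. Confidence is medium for those reasons. It should be fixed, because even on the benign reading the sentence can be carried out in two ways.

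**What to change.** Make the opening paragraph of Phase 2 and Figure 2 agree, and replace the alternation sentence with wording such as:

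> Patients will be assigned 1:1 from a computer-generated random list, stratified by VKA versus NOAC, in permuted blocks of varying size. The list is held by someone outside recruitment, and each assignment is released only after consent and the baseline survey.

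This gives the VKA/NOAC balance the sponsor wants without a predictable sequence. If balanced random assignment was all that was meant, it is enough to delete *alternate* and name the stratified list.

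The cost is one sentence, a check of Figure 2, and the small effort of preparing and holding a list. The university biostatistics department is named only for analysis, so its agreement would be needed if it is to hold the list. The 64 completers and 80 enrolled per arm stay as they are.

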**Figure 2: Tech Trial Study Group Assignment Process**

### ***i. Patient Selection***

- a) Study Population: The study population is comprised of all adult, ambulatory PPG-Cardiology patients with non-valvular atrial fibrillation who are taking an oral anti-coagulant medication
  
- a. Sample Size: Approximately 160 patients (80 Control/80 Experimental Groups; randomized/un-blinded)

\*Based on prior data, the within-group standard deviation of the medication possession ratio (MPR) is estimated to be 10%. MPR is considered a continuous variable and sample size calculations are based on comparing the difference in two mean MPR values. With a final sample size of 64 subjects per group completing the study, the study will have 80% power to detect a 5% difference in MPR between groups, assuming two-sided tests each conducted at a 5% significance level. To account for a 20% dropout rate, 80 subjects will be enrolled per group.

b) Inclusion/Exclusion Criteria:

Inclusion Criteria

1. Diagnosis of Atrial Fibrillation (Paroxysmal, Persistent, Permanent)
2. Receiving Oral Anticoagulation (VKA or NOAC) for non-valvular AF
3. Physically and Mentally capable of providing Informed Consent
4. Age 18 years or older
5. Access to Computer and Internet
6. Ability to read and understand English
7. Current Patient of PPG-Cardiology
8. Willing to have a MyChart account

Exclusion Criteria

1. Absence of History of Atrial Fibrillation (AF)
2. Does not meet Inclusion Criteria
3. Anticoagulation with VKA or NOAC for reasons other than non-valvular AF
4. Prescribed the anticoagulation medication Dabigatran, as this specific NOAC cannot be transferred from its original pill bottle to the study smart pill bottle
5. Unable to physically or cognitively carry out the tasks necessary for utilizing a PHR such as; blindness, loss of function of arms, cognitive impairments (per chart review) that would interfere in learning a new task
6. Designated as part of a vulnerable subject population that the investigator or designee identifies to have compromised autonomy related to potential study participation
7. Currently participating in another Parkview study that involves PHR use
8. Not willing to have a MyChart account

9. Previously participated in the study focus groups
10. Previously participated in the study design sessions

c) Enrollment:

A list of adult patients who meet inclusion criteria will be provided by the Anticoagulation Therapy Unit (ATU) Clinic and Parkview Physicians Group-Cardiology. An additional list of adult patients who meet inclusion criteria will be obtained from patient records at Parkview Physicians Group-Cardiology using Epic reporting tools. Research staff will also recruit participants during education sessions held by the Parkview Heart Institute, which have been funded by Boston Scientific. The research staff will be introduced by the Parkview Heart Institute coordinator, but will not present at any time during the education session. Attendees of the education sessions will be given an information folder already provided by the Parkview Heart Institute. The research team has permission to include a flyer (see attached flyer), that can be included in the folder, which provides a short summary about the study. The research team will also distribute recruitment flyers to individuals who may be interested in participating in the study that are in attendance at the education session. Those attendees who express an interest in participating will have their contact information recorded by the research team or will contact the Informatics Research Nurse coordinator as listed on the flyer. As with all possible participants, research staff will review patient charts to identify if they meet inclusion criteria, or if factors in the exclusion criteria are identified. This study will not affect patient standard of care. Before contacting patients, the study nurse coordinator will contact Parkview Physicians Group-Cardiology physicians to inform them of the study and receive permission to recruit their patients for the study. Eligible patients will be contacted by research staff during scheduled ambulatory care visits or contacted by telephone. Eligible patients may also be notified of the study through MyChart, email, or letter and directed to contact research staff by phone if interested in participating. Patients may decide to proceed with the informed consent process at the time of the office visit or schedule another appointment for the study. If the communication is by telephone, appointments will be made at a time convenient for the patient to undergo the informed consent process and patients will be mailed a copy of the informed consent to review prior to their scheduled appointment. Patients will undergo the informed consent process during their appointment and those who meet

inclusion/exclusion criteria, agree to participate in the study and sign the informed consent will be enrolled in the study.

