Parkview Research Center, under the direction of [name] [name], recently completed a two-arm randomized, prospective 6-month pilot study to explore the impact of a PHR on medication adherence and patient engagement in patients with AF who were taking the novel oral anticoagulant medication, dabigatran. Patients in that study were provided access to a PHR, Epic's MyChart. The intervention group (N=44) received one-on-one training on MyChart use and received educational newsletters about dabigatran at 4, 6 and 10 weeks via MyChart. The control group (N=41) received the standard care and PHR access without any training or health education. A survey, comprising 54 questions pertaining to technology acceptance, medication knowledge, medication adherence, and patient activation measure (PAM), was sent to both groups at the baseline and the end of study. Medication dispensing data collected from the

pharmacy where patients filled their prescriptions were used for calculating the medication possession ratio (MPR).

Results from that study revealed that knowledge of dabigatran and MPRs increased significantly in the intervention group, but not in the control group. Self-reported medication adherence also increased by 10% in the intervention group, compared to 4% in the control group. In the proposed project, we plan to develop a more robust approach to impact medication adherence with ALL types of oral anticoagulants- vitamin K antagonists (VKAs) and novel oral anticoagulants (NOACs) - that includes tailored messaging to patients via MyChart during key transitions in care such as new AF diagnosis or changes in medication. The proposed study provides an opportunity to further explore the utilization of health information technology tools in relation to self-management of AF and adherence to anticoagulation therapy.

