During enrollment, patients will be instructed to contact study staff if their anticoagulant medication is changed or permanently discontinued at any point during the study. If their anticoagulant medication is permanently discontinued, patients will be instructed to stay in the study even while they are not taking their anticoagulant. Sometimes patients' anticoagulation therapy is temporarily discontinued for surgery or other health reasons. In order to maximize patient safety when these temporary holds on medications occur, tailored messages related to medication administration and compliance will include a disclaimer that if their medication has been stopped then this information is supplementary and they should follow their doctor's instructions first and foremost.

Concurrent with the educational messages sent to patients through MyChart, patients will periodically be sent a short survey asking them to evaluate the health information they just received. These questions will enable patients to evaluate the content, timing and delivery format of the interventional messaging. The survey will be administered through Survey Monkey, and the MyChart message will contain a secure link to access the survey.

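### The MPR comparison is sized without adjustment and with no reserve, on an SD whose carry-over to this population is not justified; adjusting for prior refills and drug class would gain precision at no cost in patients

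*Protocol*

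**What the plan says.** The sample size note in the Protocol (Phase 2, i. Patient Selection) treats the medication possession ratio (MPR) as continuous and sizes the trial on the difference between two means. Its inputs are:

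- **SD:** "the within-group standard deviation of the medication possession ratio (MPR) is estimated to be 10" per cent, credited to prior data with references 4 to 8. No study-level SD, sample size or range is given.
- **Power:** "With a final sample size of 64 subjects per group completing the study, the study will have 80% power to detect a 5% difference in" that ratio.
- **Test:** "assuming two-sided tests each conducted at a 5% significance level".
- **Enrolment:** "To account for a 20% dropout rate, 80 subjects will be enrolled per group".

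Four other places bear on this:

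- **Study Background** describes one earlier anticoagulant study with MPR as an outcome. It enrolled "patients with AF who were taking the novel oral anticoagulant medication, dabigatran", with 44 in the intervention group and 41 in the control group. No SD is reported.
- **Phase 2 exclusion criterion 4** removes patients "Prescribed the anticoagulation medication Dabigatran, as this specific NOAC cannot be transferred from its original pill bottle". The inclusion criteria admit VKA users and users of the other NOACs.
- **The opening paragraph of Phase 2** says that allocation is meant to balance VKA and NOAC users across the two groups.
- **Table 3** lists prescription refill frequency for the 6 months before baseline as well as for the trial period.

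**The concern.** The whole sizing depends on one SD, and the Protocol gives no reason why that SD applies to the patients to be enrolled. By their titles, references 4, 5, 6 and 8 concern cardiovascular disease in general, coronary disease, care after coronary intervention and implantable defibrillators. Only reference 7 names adherence in atrial fibrillation. The one anticoagulant study described in the text enrolled users of a drug that bars entry here. The value may still be right, but the stated 80% power reads as a property of the design when it depends on an assumption brought in from other populations.

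The calculation also has no margin and leaves free precision unused. It assumes an unadjusted comparison, although the trial collects the same patients' refill history before baseline and balances allocation on drug class. A baseline measure of the outcome behaviour is usually the most useful covariate available. If the SD is somewhat above 10, the unadjusted comparison falls short of its target, and a null result quoted beside 80% power could be given more weight than it deserves.

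**Working it through.** **Inputs from the Protocol:** SD 10 points; difference 5 points; two-sided 5% level; 64 completers per group; 20% dropout; equal allocation.

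**1. Reproduce the stated figure.** For a two-sample t-test:

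- Standard error of the difference = SD × √(2/n) = 10 × √(2/64) = 1.768.
- Noncentrality = 5 / 1.768 = 2.83 on 126 degrees of freedom.
- Power = 80.1%. Solving for 80% power gives n = 63.8, so 64 per group.
- Enrolment = 64 / 0.80 = 80 per group, 160 in total.

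The Protocol's figures reproduce exactly.

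**2. Reserve.** The difference detectable with 80% power (normal approximation) is (1.960 + 0.842) × SD × √(2/64). At SD 10 this is 4.95 points against a target of 5. At SD 12 it is 5.9 points and at SD 15 it is 7.4. There is practically no slack at the planned SD.

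**3. Dependence on the SD.** The documents give no SD for the enrolled population, so values other than 10 are assumptions, shown on both sides of it. The difference (5 points) and n (64 per group) stay fixed.

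**4. Effect of adjustment.** With a baseline covariate correlated r with the outcome, the residual SD is SD × √(1 − r²). The factor is √0.75 = 0.866 at r = 0.5 and √0.64 = 0.80 at r = 0.6. These correlations are assumptions; the documents give none. The same t-test formula with the residual SD ignores the few degrees of freedom spent on covariates, which is negligible with 128 completers.

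| SD of MPR | Unadjusted power | Residual SD (r = 0.5 / 0.6) | Adjusted power (r = 0.5 / 0.6) |
|---|---|---|---|
| 8 | 94% | 6.9 / 6.4 | 98% / 99% |
| 10 | 80% | 8.7 / 8.0 | 90% / 94% |
| 12 | 65% | 10.4 / 9.6 | 77% / 83% |
| 15 | 46% | 13.0 / 12.0 | 58% / 65% |

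Adjustment roughly makes up for an SD of 12. It does not make up for an SD of 15. Any gain from also including drug class is not counted, because the documents give no class-specific MPR.

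**The case against.** **Nothing in the sample size note is miscalculated.** It names its input, calls it an estimate, cites sources and does the arithmetic correctly. That a planning SD may prove optimistic can be said of almost any trial. This stands, and it is why the point is not that the power is wrong.

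**The source of the SD cannot be seen.** Five reports are cited, and the documents do not say which supplied the 10 per cent or whether it was pooled. That reference 7 is the dabigatran study in Study Background is inferred from its title and the description. This also stands. It means that the SD cannot be called a dabigatran-only figure. It does not supply the missing justification, because the other four titles are further from anticoagulant users.

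**A reader might infer that the true SD must exceed 10, so that power is below 80%.** Two features invite this. Warfarin users are added, and after permanent discontinuation "patients will be instructed to stay in the study even while they are not taking their anticoagulant". Neither shows a larger SD. The Protocol says that warfarin doses need calibration, but does not link this to variation in MPR. It also treats INR monitoring as a marker of compliance and fears poorer adherence on the novel agents. Retained stoppers inflate the SD only if MPR runs over the full 6 months after stopping. If it is censored at discontinuation they do not, and the Protocol does not fix this. Other features could narrow the spread: patients need internet access and willingness to use MyChart, those with interfering cognitive impairment are excluded, and all use a monitored bottle. An SD of 8 is as undocumented as an SD of 12.

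**Taking prescriber-ordered off-treatment days out of the MPR denominator may look like a remedy.** I do not recommend it. It would depend on documentation after randomisation in an unblinded trial. Patients themselves report changes to staff, and only one group receives continuing messages, so unequal reporting could bias the outcome.

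**Covariate adjustment is ordinary SAP content, and a two-means sizing does not rule it out.** That is fair, and its absence from the Protocol is not an error. The case for naming it here is that it costs nothing and bears directly on a power statement that has no margin.

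**Conclusion.** The stated 80% power is arithmetically correct and conditional on an SD whose transfer to this population the Protocol does not justify. Over an assumed SD range of 8 to 15, unadjusted power at 64 per group runs from 94% down to 46%. The documents do not place the true SD within that range, so the conclusion is that the figure is unsupported beyond SD 10, not that the trial is underpowered.

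The actionable part is the unused precision. Adjusting for prior-6-month refill adherence and drug class raises power at SD 10 from 80% to 90–94%, and at SD 12 from 65% to 77–83%, if the correlation with prior adherence is 0.5 to 0.6. That correlation is an assumption. The prior measure is refill frequency from the electronic record, and patients new to treatment will have little or no history, so the gain could be smaller. With a weak correlation the cost is only a few degrees of freedom. This is an improvement worth making, not the correction of an error.

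**What to change.** In the sample size note of Phase 2, i. Patient Selection:

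1. **Name the analysis.** State the MPR comparison as a linear model of 6-month MPR on randomised group, adjusted for refill adherence in the 6 months before baseline, with an indicator for patients with no prior fills, and for drug class at baseline (VKA or NOAC).
2. **Make the power conditional.** State that 64 completers per group give 80% power for a 5-point difference if the SD is 10, and add the range from the unadjusted t-test: 94% at SD 8, 65% at SD 12 and 46% at SD 15. Any adjusted figures should be quoted with their assumed correlation.
3. **Give the source of the SD.** Say which cited report or reports supplied the 10 per cent, and why it is expected to hold for VKA users and users of NOACs other than dabigatran.

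The enrolment target stays as planned ("Approximately 160 patients (80 Control/80 Experimental Groups; randomized/un-blinded"). No data are needed beyond what Table 3 lists, and the MPR denominator is left alone. The cost is protocol wording and a power statement that becomes conditional and may look less favourable.
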